#### Monitoring of Probe Site

- Each neonate will have the area surrounding the mepitel and probe assessed daily for erythema or skin changes by the RN taking care of that baby.

#### Measurement of Rsat and Csat

- Rsat and Csat levels will be measured continuously for the first 7 days of age
- Sensors will be used for as long as a value returns without signal degradation (average 4 days)
- Clinicians will be blinded to the saturation values

#### Record Review

- Medical records will be reviewed for neonatal, perinatal, and maternal demographics. Vital sign information, labs, medications and imaging results will also be recorded. This data will be used to correlate NIRS values to a variety of perinatal and neonatal factors: vitals, labs, medications, hospitalization events, imaging studies. This data will hopefully inform future research on possible interventions to improve NIRS values in subsequent populations of preterm neonates.

12.6 What is the anticipated DURATION of your project or study?

12-18 months depending on subject recruitment

12.7 \* Does your research involve biospecimen collection?

Yes  No

12.8 Does your research involve extracting and storing data from medical records?

Yes  No

#### 13.0 Record Review Details

13.1 Enter the date range for the data you plan to collect (e.g. 1/1/2010 - 12/31/2015).

From:

01/01/2018

To:

12/31/2018

13.2 How many records do you plan to access at UnityPoint Health - Meriter?

## 13.3 Will you be using records from other institutions?

Yes  No

In the text box below, list the institutions for all the records you plan to use. Give the approximate number of records from each institution.

**For Example:**

- 100 records from the Wisconsin State Department of Health and Human Services
- 50 Records from UW Hospital and Clinics
- 500 records from Marshfield Clinic

## 13.4 Does your record review research involve matching subject data from more than one medical record system?

Yes  No

If YES, list the medical record systems involved and explain the methods you will use to match subject data.

## 13.5 Will the data collected be used for purposes other than those described in this application?

Yes  No

Yes  No

## 14.0 Record Review Support Documents

## 14.1 Data Research Summary Form

**MANDATORY - You must complete and upload this form to your submission.**

- Get the **Data Research Summary Form** [HERE](#).
- **Download** the form to your computer.
- **Complete** the form, following the instructions on the lower left tab in the excel workbook. Put a version number and date in the top left cell (A1). This should match what you enter in the iRIS upload screen.
- **Add** the completed form later in the Initial Review Submission Packet in the Other Study Documents section.

## 14.2 Health Information Management Endorsement

Will subjects sign a consent document that allows you to access their records for research purposes?

Yes  No

If you answered NO above, follow the MANDATORY directions below.

**MANDATORY** for access to Meriter-UnityPoint Health Records **for RESEARCH purposes** without subjects' consent.

- Get the **Patient Records Endorsement Form** [HERE](#).
- **Download** the form to your computer.
- **Complete** the form following the instructions on page 1.
- **Add** the completed **signed** form later in the Initial Review Submission Packet in the Other Study

Documents section.

### 14.3 DATA SECURITY for Non-employees

Are you a UnityPoint Health - Meriter employee?

**HINT:** If your paycheck doesn't come from a UnityPoint Health entity, you are not an employee.

Yes  No

If you answered NO above, follow the MANDATORY directions below.

**MANDATORY** for those **not** employed by a UnityPoint Health entity.

If you plan to store study data that includes patient identifiers on a non-Meriter server or a non-Meriter device, your plan must be endorsed by the UnityPoint Health - Meriter IT Security Officer.

- Get the **Electronic Data Security Endorsement** [HERE](#).
- **Download** the form to your computer.
- **Complete** the form, following the directions at the top of the page.
- **Send** the **Electronic Data Security Endorsement** (requires signature) with the **Data Research Summary** form to the **IT Security Officer** for signature.
- **Add** the completed **signed** form later in the Initial Review Submission Packet in the Other Documents section.

### 15.0 Study Population

#### 15.1 \* Age

Select all that apply:

- 0-6 (parental consent only)  
 7-11 (Requires child's assent plus parental permission)  
 12-17 (Requires consent plus parental permission)  
 18+ (Requires consent only)

**Enter the specific age range for study population (if overlap or specific within a category):**

0.00

to

1.00

months

years

#### 15.2 \* Gender

- Male  
 Female  
 Both male and female

#### 15.3 Is any racial/ethnic group excluded?

Yes  No

15.4 \* What is the number of participants, biological samples, or records you are planning to enroll or review at UnityPoint Health - Meriter?

60

If necessary, provide explanation below:

15.5 \* What is the number of participants, biological specimens, or records that will be enrolled or reviewed at all sites?

60

If necessary, provide explanation below:

15.6 \* Justification for the number of subjects, specimens or records required. Include information about the statistical analysis of your data.

**Study Population:**

In order to have the ability to identify a difference of renal NIRS in preterm patients with AKI and preterm patients without AKI, a total of 60 patients will need to be enrolled. At the time of enrollment all subjects will be 'normal' without evidence of AKI. The majority of these patients will likely end up to be preterm patients without AKI given an average rate of AKI in the first week of life of 15%. However, with only 9 patients in the AKI group and 51 in the no AKI group, we will have the statistical power necessary to detect a 10 point renal NIRS difference in these groups.

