**12.0 Research Design & Procedures**

**12.1 \* Please list all departments, nursing units, etc. that will be involved at Meriter Hospital (e.g. blood bank, 6 North nursing unit, etc.). Enter the name of the person your study team has been in contact with for each area. Read the HELP Bubble in the right panel for more information.**

Department / Nursing Unit	Contact Person
7N, Neonatal ICU	[name] and [name]

**12.2 PURPOSE** What is the objective or purpose of your study? If you have specific aims, list them here. At the end of each paragraph hit Enter. Then hit Shift + Enter.

Specific Aim 1: To determine if a reduction in renal NIRS in preterm neonates correlates with current markers of neonatal AKI (decreased urine output or increased serum creatinine) in the first 7 days after birth.

Specific Aim 2: To determine if there is a significant reduction or increase in renal NIRS due to the use of medications in the NICU.

12.3 BACKGROUND What prior information or knowledge exists to support the conduct of this project or study? At the end of each paragraph hit Enter. Then hit Shift + Enter.

Preterm birth (< 37 weeks gestation) currently occurs in 1 in 8 deliveries and the majority of these infants are born with a low birth weight (LBW; <2.5kg), with many having a very low birth weight (VLBW; <1.5 kg). Although LBW is a well recognized risk factor for developing chronic kidney disease (CKD), prematurity and VLBW status have only recently been shown to be associated with later onset CKD. Children born preterm or with a VLBW are most at risk for developing CKD due to incomplete nephrogenesis, neonatal nephrotoxin exposures, and acute kidney injury (AKI) secondary to complex neonatal intensive care unit (NICU) hospitalizations. In 2013, Wisconsin had over 5,000 babies born preterm- over 600 of which were born with a VLBW. If you combine VLBW and LBW babies, the number of children at risk for developing CKD born each year in Wisconsin is over 1200.

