Chronic kidney disease is a widespread public health epidemic associated with increased risks of cardiovascular disease and death. In Wisconsin, CKD has increased 3 fold since 1982 with early stage CKD now affecting over 40,000 and late stage CKD affecting over 3,000 in the state. Along with the rising incidence of CKD there have been associated increased costs – since 1993 the costs of caring for patients with CKD have increased 5 fold nationally. **The long-term goal of my research is to evaluate the contribution of preterm birth, NICU exposures and specifically AKI to the development of CKD in childhood and adulthood.** This past year I published a paper comparing the renal function of former preterm infants at 5 years of age. In this research study we found that preterm patients with a history of AKI in the NICU were 4 times as likely to have signs of CKD compared to those without a history of AKI in the NICU. This was consistent with pediatric and adult literature that has shown increased risk of CKD following an episode of AKI. It is clear from these studies that AKI is a significant risk factor for development of CKD and prevention of AKI should be a focus of all intensive care unit patients.

Acute kidney injury in the NICU is not only associated with long term development of CKD, but also with acute morbidity and increased rates of mortality. With AKI occurring in 12 to 40% of preterm infants, it is a common occurrence, particularly in the smallest and most preterm patients. The diagnosis of AKI in the NICU is currently based off of a standardized definition of increases in serum creatinine or decreases in urine output. Unfortunately, each of these criteria generally change hours to days after the initial insult resulting in the AKI band changes in therapy are generally not made until after the diagnosis. Multiple studies have examined the use of urinary biomarkers to diagnose AKI and many of these are promising for early detection of AKI- but these also are most often seen after the kidney injury. Ideally changes in blood flow or oxygenation of the kidneys could be detected prior to injury and this would allow clinicians to change therapy immediately.

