Recently there has been increased use of a device to detect tissue oxygenation. Near infrared spectroscopy (NIRS) is a non-invasive skin-monitoring device used on patients to determine regional tissue oxygenation. Sensors can be placed in multiple locations, but most commonly the head, abdomen or flank are used to reflect brain, gut and kidney oxygen levels respectively. Studies in animals, pediatric and adult patients have shown that NIRS can be used to detect flow-induced changes in oxygen levels in the kidneys. In preterm neonates, a recent study showed that renal NIRS can be used to diagnose a hemodynamically significant PDA, a risk factor for AKI in nearly all neonatal AKI studies. In term neonates renal NIRS has been used in intra and post-operative cardiac surgery patients to detect AKI and has correlated with changes in both serum creatinine and urinary biomarkers. However, no studies currently exist demonstrating the correlation with urinary output or serum creatinine (the markers used for the current definition of AKI) and NIRS monitoring in preterm infants.

NIRS monitoring has been shown to be safe in multiple preterm studies. The sensor is both a light source and a detector used to measure the absorption of light by oxygenated and deoxygenated hemoglobin in the tissue. The sensor generates no heat and lasts between 1-4 days before needing to be changed. Normal renal NIRS values have been demonstrated in a number of small cohort studies and there are a number of factors that can affect the normal values: gestational age, post-menstrual age and hemoglobin. Given the large inter-individual variability, several different definitions have been used to define a low renal NIRS value: < 25% baseline, > 15 points below baseline and < 65%.

Given that AKI is common in preterm infants, can lead to long-term CKD, and current methods of diagnosis occur after injury, we propose that NIRS monitors can identify AKI in real time that may result in decreased rates of AKI and improved long-term outcomes.

12.4 ENROLLMENT Describe how subjects will be identified, and enrolled in the study. Indicate if randomization occurs and/or how subjects are assigned to study arms or groups if applicable. At the end of each paragraph hit Enter. Then hit Shift + Enter.

Goal Enrollment: 60 preterm patients

Eligibility: All preterm infants < 32 weeks admitted to Meriter UPH NICU

Inclusion Criteria:

1. Preterm neonate < 32 weeks

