**Statistical Power calculation:**

renal NIRS average for AKI group = 60

renal NIRS average for non-AKI group = 70

Standard deviation for AKI group = 10

Standard deviation for non-AKI group = 10

5% alpha

50% beta

Power calculation for the above would require at least 5 patients in each group.

With a rate of AKI of 15%, out of 60 patients there would be 9 in the AKI group and 51 in the no AKI group.

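### Aim 1 asks about a reduction in renal NIRS, but 15.6 sets out only a raw AKI v no-AKI difference in averages; gestational age can confound it in either direction, and adjusting for it needs no new data

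*Combined protocol and SAP*

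**What the plan says.** Specific Aim 1 (12.2) is "To determine if a reduction in renal NIRS in preterm neonates correlates with current markers of neonatal AKI", the markers being lower urine output or higher creatinine over the first week.

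The prompt of 15.6 asks for the sample-size justification and adds: "Include information about the statistical analysis of your data". The answer aims at a contrast between groups: "In order to have the ability to identify a difference of renal NIRS in preterm patients with AKI and preterm patients without AKI". It then gives "renal NIRS average for AKI group = 60", 70 for the other group, an SD of 10 in each, 5% alpha, 50% beta and an expected split of 9 v 51. It names no test, model, baseline or covariate.

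The Background (12.3) describes normal renal NIRS as subject to "a number of factors that can affect the normal values: gestational age, post-menstrual age and hemoglobin". It adds: "Given the large inter-individual variability, several different definitions have been used to define a low renal NIRS value". Two of the three definitions it lists are relative to the infant's baseline; none is chosen. On AKI it says that "it is a common occurrence, particularly in the smallest and most preterm patients".

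Record Review (12.5) plans to correlate NIRS with many perinatal and neonatal factors. It gives no method and does not mention adjusting the AKI comparison.

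**The concern.** The protocol itself links gestational age to both sides of the comparison: to the NIRS level and to the risk of AKI. A raw difference in averages can then mix kidney injury with immaturity.

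If less mature infants have lower normal values, part of a low AKI average could be read as injury. If they have higher normal values, a real fall could be masked. The Background says only that gestational age has an effect, so neither can be ruled out.

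A difference in averages also cannot tell a fall from a level that was low from the start. The word reduction in Aim 1 is therefore left without an analysis.

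**Working it through.** **Inputs from 15.6:** averages 60 and 70, SD 10, alpha 5%, beta 50%, groups of 9 and 51. Sidedness is not stated; I use two-sided tests below.

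**Assumed, because the documents give no values:** the gestational-age gap g between groups (1, 0.5 or 0.25 SD), the within-group correlation r of gestational age with NIRS (0.2, 0.3, 0.4), and the within-group correlation ρ of early with later NIRS.

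**1. The plan's own figures.** n per group = 2(z for alpha + z for power)² × (SD/difference)². At 50% power the second z is 0. One-sided: 2 × 1.645² = 5.41. Two-sided: 2 × 1.960² = 7.68. The stated 5 is close to the one-sided result (6 when rounded up); two-sided gives 8. The split is 0.15 × 60 = 9. Nothing below depends on the figure of 5.

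**2. Unadjusted power.** SE = 10 × √(1/9 + 1/51) = 3.616, and 10/3.616 = 2.766. Noncentral t with 58 df gives 77.6%.

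**3. Size of the confounding.** Shift in the raw difference = r × 10 × g points. With r = 0.3 and g = 1 the shift is 3 points, and 3/3.616 = 0.830. The same t calculation then gives two results: the chance of a significant result when AKI has no effect (bias in the direction of the hypothesis), and the power for a true 10 points when the shift is subtracted (bias in the other direction).

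| Gap g | Shift at r = 0.2 / 0.3 / 0.4 | False positive, unadjusted | Power if bias is opposite |
|---|---|---|---|
| 1 SD | 2 / 3 / 4 | 8 / 13 / 19% | 59 / 48 / 37% |
| 0.5 SD | 1 / 1.5 / 2 | 6 / 7 / 8% | 69 / 64 / 59% |
| 0.25 SD | 0.5 / 0.75 / 1 | 5 / 5 / 6% | 73 / 71 / 69% |

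Simulation of the 1-SD case (20,000 runs per setting) gave 5% false positives once gestational age was in the model. Early NIRS without gestational age left 6 / 7 / 9% (ρ = 0.5).

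**4. Cost of adjusting for gestational age.** The SE is multiplied by √(1 − r²) and by √(1 + pq g²), with p = 0.15, q = 0.85 and pq = 0.1275; df 57. At g = 1, power for 10 points is 73 / 74 / 77 / 80% at r = 0 / 0.2 / 0.3 / 0.4, against 78% unadjusted.

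**5. Adding early NIRS.** The SD becomes 10 × √(1 − ρ²), with the same 1.1275 variance inflation and 56 df. Gestational age is given no further explanatory value.
- Power is 77 / 84 / 95% at ρ = 0.3 / 0.5 / 0.7.
- It beats the unadjusted test only if ρ exceeds about 0.34 / 0.33 / 0.31 with 9 / 8 / 7 AKI infants, comparing the two tests at equal numbers.
- A change score, with SD 10 × √(2(1 − ρ)) and no covariate, has 63 / 78 / 94% power. With early NIRS alone as a covariate the figures are 81 / 88 / 97%.

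**6. If the early reading is already lowered.** Adjusting removes ρ times the early fall. With ρ = 0.5 and a 5-point fall, 10 − 0.5 × 5 = 7.5 points remain. Power is then about 65% with early NIRS alone and 60% with both covariates. Allowing also for the groups differing in early NIRS lowers each by about 1 point.

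**The case against.** The strongest reply is that 15.6 is mainly a sample-size box, and a two-means calculation is a common simplification there. A reader might infer that the investigators have committed to an unadjusted analysis. The documents do not support that: they set out one contrast and leave the analysis of Aim 1 otherwise unspecified. The point that stands is narrower. The prompt asks for the analysis, this is the only AKI comparison given, and the correlations planned in Record Review do not adjust it.

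A reader might also infer that confounding would produce a false link with kidney injury. That needs less mature infants to read lower, which the Background does not say.

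The 1-SD gap is a strong scenario. The cohort is already restricted to births before 32 weeks, so the contrast in maturity may be small; at 0.25 SD the false-positive rate hardly moves.

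Finally, one could argue that early NIRS belongs in the main model because Aim 1 concerns a fall. Against that, 12.4 allows the sensor to go on at any time before 48 hours of age, and 12.3 and 17.7 say the AKI markers lag injury by hours to days. The first readings may already reflect injury, even though 15.6 describes infants as free of evident AKI at enrollment. That objection stands, and it is why early NIRS should be secondary.

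**Conclusion.** The concern holds in a limited form. The sole AKI comparison on paper ignores a factor that the protocol ties to both AKI and renal NIRS, and it does not address reduction.

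The possible size ranges from negligible (5 to 6% false positives at a 0.25-SD gap) to material (8 to 19% at 1 SD, or power of 59 to 37% if the bias runs the other way). All gaps and correlations are assumptions, and so are the two-sided test and an AKI count of exactly 9.

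The case for adjusting is less confounding, not more power. At a 1-SD gap, power changes from 78% to between 73 and 80%. Nor should a reader infer that losing AKI infants makes the two-covariate model unfavourable: at equal numbers the break-even correlation stays near 0.3. This should be corrected before analysis, but it does not prevent the study from running.

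**What to change.** Add to 15.6:

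*The main Aim 1 comparison is a linear regression of each infant's mean renal NIRS on AKI status (yes/no) in the first 7 days, adjusted for gestational age. The unadjusted difference is reported beside it. A secondary model adds the infant's own early renal NIRS, the mean of a fixed first block of recording whose length is set before analysis.*

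The secondary model is the one that speaks to reduction. Early NIRS enters it as a covariate rather than through a change score. With about 9 AKI infants the covariate list must stay short, so hemoglobin, which the Background also names, fits better in a sensitivity model. The yes/no status also needs its thresholds written down: 12.3 refers to a "standardized definition of increases in serum creatinine or decreases in urine output" without giving them.

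**Cost.** No new data or patients are needed: renal NIRS is recorded to day 7 (12.5), and gestational age is an entry criterion (15.8) and is listed in 24.2. Only analysis text changes. The downsides are a possible loss of up to about 5 points of power from the gestational-age term (78% to 73%), and a larger loss in the secondary model if injury precedes the first block. A mean over the whole recording also mixes readings before and after AKI and dilutes a short fall, as the unadjusted average would.

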**Statistical Power calculation:**

renal NIRS average for AKI group = 60

renal NIRS average for non-AKI group = 70

Standard deviation for AKI group = 10

Standard deviation for non-AKI group = 10

5% alpha

50% beta

Power calculation for the above would require at least 5 patients in each group.

With a rate of AKI of 15%, out of 60 patients there would be 9 in the AKI group and 51 in the no AKI group.

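### The stated minimum of 5 patients in each group does not reach the plan's own 50% power if the groups are equal, and the power of the planned 9 v 51 split is not stated

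*Combined protocol and SAP*

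**What the plan says.** Section 15.6, under Statistical Power calculation, gives four numerical assumptions: "renal NIRS average for AKI group = 60", "renal NIRS average for non-AKI group = 70", and a standard deviation of 10 in each group. It adds 5% alpha and 50% beta, and states: "Power calculation for the above would require at least 5 patients in each group". It then applies the AKI rate and says that "out of 60 patients there would be 9 in the AKI group and 51 in the no AKI group".

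The paragraph before it, under Study Population, sets total enrolment at 60, cites "an average rate of AKI in the first week of life of 15" per cent, and says that "with only 9 patients in the AKI group and 51 in the no AKI group, we will have the statistical power necessary" to detect a 10-point difference. It gives no power figure for that split.

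Neither paragraph names a statistical test, says whether alpha is one- or two-sided, or gives the allocation ratio behind the 5. The wording elsewhere does not settle sidedness. Study Population speaks of the ability "to identify a difference of renal NIRS in preterm patients with AKI and preterm patients without AKI", which has no direction. Specific Aim 1 in section 12.2 is directional: "To determine if a reduction in renal NIRS in preterm neonates correlates with current markers of neonatal AKI".

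**The concern.** This is the plan's only sample-size calculation, and section 15.6 is where the form asks for the number of subjects to be justified. With a standardised difference of 1 and no allocation ratio given, a minimum in each group is normally read as equal groups. On that reading 5 looks too small even for a target as low as 50%.

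The calculation is also not carried through to the design the study expects. The 5 rests on 50% power, the study expects 9 v 51, and no power is attached to 9 v 51. A reader cannot tell how the adequacy claim in Study Population was reached. The only power visible, 50%, is lower than the expected split would have on the plan's own inputs.

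**Working it through.** **Inputs (all from section 15.6).** Means 60 and 70, so the difference is 10. SD 10 in both groups, so d = 10/10 = 1. Alpha 0.05. Beta 0.50, so target power is 0.50 and z for power is 0. AKI rate 15%, N = 60, expected split 9 v 51.

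**Assumptions the plan does not supply.** One renal NIRS value per infant; a two-sample comparison of means; both sidedness options tried.

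**Step 1. Try to reproduce the 5 with equal groups.** By the normal formula, n per group = 2(z_alpha + z_power)² / d², with z_power = 0.
- Two-sided: 2 × 1.96² = 7.68, rounded up to 8.
- One-sided: 2 × 1.645² = 5.41, rounded up to 6.

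By the noncentral t distribution, the smallest equal groups reaching 50% are 9 (two-sided; 8 v 8 gives 46.1%, 9 v 9 gives 51.3%) and 7 (one-sided; 6 v 6 gives 48.8%, 7 v 7 gives 54.7%). No variant gives 5 when rounded up.

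**Step 2. Power of 5 v 5.** The noncentrality is d / √(1/5 + 1/5) = 1.581.

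| 5 v 5 | z | equal-variance t (8 df) |
|---|---|---|
| two-sided | 35% | 28.6% |
| one-sided | 47.5% | 42.1% |

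All four are below 50%. The one-sided z case misses by 2.5 points.

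**Step 3. Where a 5 could come from.** Two routes give it, and the documents confirm neither.
- One-sided normal formula, equal groups: 5.41 rounded to the nearest whole number is 5. This fits the words about each group, but rounding down leaves the 47.5% of step 2.
- Unequal groups at the plan's 9:51 (15:85) ratio, two-sided normal formula, for the smaller group: (1 + 9/51) × 1.96² = 4.52, rounded up to 5. The larger group is then 5 × 85/15 = 28.3, about 28. Power of 5 v 28 is 51.4% (equal-variance t) or 54.0% (z) two-sided, but about 41% by Welch's test (simulation). The one-sided version at this ratio gives (1 + 9/51) × 1.645² = 3.18, rounded up to 4.

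**Step 4. The 5 as a floor for the smaller group when N = 60.** 5 v 55: noncentrality 1 / √(1/5 + 1/55) = 2.141; two-sided power 55.8% (equal-variance t) or 57.2% (z).

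**Step 5. Power of the planned split.** 9 v 51: noncentrality 1 / √(1/9 + 1/51) = 2.766.

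| 9 v 51 | power |
|---|---|
| equal-variance t, two-sided | 77.6% |
| z, two-sided | 79.0% |
| Welch, two-sided (simulation) | 71% |
| equal-variance t, one-sided | 86.2% |

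The number of AKI cases is not fixed by design. With the count taken as Binomial(60, 0.15), the two-sided equal-variance t power averages 75.0%.

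**The case against.** The strongest reply is that nobody proposes 5 v 5. Enrolment is fixed at 60 in sections 12.4, 15.4, 15.5 and 15.6, the sentence says at least, and the next line gives 9 v 51. Read in that setting, 5 can be taken as a floor for the smaller group, and 5 v 55 clears 50% power (step 4). This much stands: the line does not mislead anyone about how many infants will be enrolled, and a reader who infers that it endorses a study of 10 goes beyond the documents. What remains is that the sentence says each group, and on those words the figure falls short.

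A second reply is that Aim 1 is directional, so a one-sided normal calculation rounded to 5 is plausible and the error is one infant per group. That is fair as a possibility. It means one cannot say that 5 makes sense only as an AKI-group size. A stated minimum should still meet its own target, and 47.5% does not.

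It is equally tempting to treat the 15:85 ratio as the true origin and to correct the sentence accordingly. The documents do not support that either. The calculation states the 5 before it brings in the 15% rate, and the match depends on choosing two-sided, z and that ratio together.

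Finally, omitting the power of 9 v 51 is a gap in reporting and not an arithmetic error. That is correct, and it limits the weight of the point.

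**Conclusion.** As written, the minimum of 5 in each group is wrong for equal groups: 5 v 5 has 29% to 47.5% power against a stated 50%, depending on test and sidedness, and equal groups need between 6 and 9. How the 5 was obtained cannot be determined from the documents.

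A reader might infer that the study is underpowered or that 60 infants are too few. The plan's own inputs do not support that. The expected 9 v 51 split has about 71% to 86% power across the tests considered, and about 75% for the two-sided equal-variance t-test once the AKI count is allowed to vary. The adequacy claim in Study Population therefore holds against the 50% target; its size is simply not stated.

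These results rest on the plan's means, SDs and 15% rate being right, and on one NIRS value per infant. The point is minor: one stated figure needs correcting and one missing figure needs adding.

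**What to change.** Keep N = 60. In section 15.6:

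- Replace the line giving 5 in each group with the power of the expected 9 v 51 split for a 10-point difference and SD 10, naming the test and sidedness the investigator chooses. The figures are about 78% for a two-sided equal-variance t-test, 71% for two-sided Welch, and 86% for a one-sided equal-variance t-test.
- Say that the AKI count is random. For the two-sided equal-variance t-test, power averaged over it at a 15% rate is about 75%.
- Confirm whether a beta of 50% was intended.
- If a minimum group size is kept, state the allocation ratio, test and sidedness it rests on.

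The cost is a rewording of a line or two and a commitment to a test and sidedness that the plan currently leaves open. Enrolment and procedures do not change.
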